6.2.4 Definitions of dose limiting toxicities (DLTs)

A dose-limiting toxicity (DLT) is defined as an adverse event or abnormal laboratory value of CTCAE Grade ≥ 3 assessed as unrelated to disease, disease progression, inter-current illness, or concomitant medications that occurs within the first two cycles of treatment with the combination treatment and meets any of the criteria included in [Table 6-3](#).

Emerging data from the new field of immune-immune combination studies suggest that some immune-related adverse events have a prolonged latency ([Wolchok 2013](#)). As such, the DLT window for the combination cohort in this trial is extended to the length of two cycles or 42 days.

National Cancer Institute Common Terminology Criteria for Adverse events (NCI CTCAE) version 4.03 will be used for all grading. For the purpose of dose-escalation decisions, DLTs will be considered and included in the BLRM.

The investigator must notify the Sponsor immediately of any unexpected CTCAE Grade ≥ 3 adverse events or laboratory abnormalities. Prior to enrolling patients into a higher dose level, CTCAE Grade ≥ 2 adverse events will be reviewed for all patients at the current dose level.

DLTs include any adverse event of CTCAE Grade 3 or higher occurring in the first two cycles of treatment during the Phase Ib dose escalation part of the study, for which relationship to study treatment cannot be ruled, with the exceptions defined in [Table 6-3](#).

Table 6-3 Criteria for defining dose-limiting toxicities

For the purpose of dose escalation and cohort expansion, DLT will be defined as follows: Any Grade 4 AEs will be considered DLTs with the exception of:
Neutropenia lasting ≤ 5 days that is not associated with fever or other clinical symptoms.
Lymphopenia or leukopenia at any grade
Any Grade 3 AEs will be considered DLTs with the exception of:
Electrolyte abnormalities that are not associated with clinical sequelae and are corrected to \leq Gr1 with appropriate management or supplementation within 72 hours of onset.
Infusion reaction that resolves to \leq Grade 1 within 6 hours.
Nausea and vomiting persisting for < 2 days with optimal anti-emetic therapy.
Thrombocytopenia without significant bleeding.
Diarrhea persisting for < 2 days with optimal anti-diarrhea therapy.
Hypertension persisting < 7 days with optimal therapy.
Infection or fever in the absence of neutropenia persisting < 7 days.
Rash or photosensitivity persisting < 7 days after treatment.

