Fatigue lasting < 7 days.
Immune-related adverse events persisting at Grade3 < 7 days after treatment with corticosteroids.
*CK elevation without associated muscle damage per investigator discretion
*Isolated AST elevations (without bilirubin or ALT elevations \geq Grade 1)
The following Grade 2 AEs will be considered as DLTs:
Total bilirubin $> 2 \times$ ULN with \geq CTCAE Grade 2 AST/ALT.

Pneumonitis persisting > 7 days despite treatment with corticosteroids.
Eye pain or reduction of visual acuity that does not respond to topical therapy and does not improve to Grade 1 severity within 2 weeks of the initiation of topical therapy OR requires systemic treatment.
Other clinically significant toxicities, including a single event or multiple occurrences of the same event may be considered as DLT's.
* MCS110 treatment results in CK and AST elevations without any association to muscle damage (Radi 2011). The CK/AST elevations are caused by reduced clearance rate from the circulation due to the diminished numbers of macrophages (Kupffer cells) in the liver (Section 1.2.2.1).

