6.3 Dose modifications

6.3.1 Dose modification and dose delay

For patients who do not tolerate the protocol-specified dosing schedule, dose adjustments are permitted in order to allow the patient to continue the study treatment, except during the first two cycles when dose modifications are only allowed if the patient experiences a DLT. The following guidelines need to be applied:

- If a patient experiences an AE meeting the criteria for DLT as outlined in Section 6.2.4, treatment should be withheld. Dose modifications for toxicities related to the study medication are summarized in Table 6-4. Following resolution of the toxicity to Grade 1 or to the patient's baseline value, the patient may resume study treatment at a lower dose level than is being tested at that time (on the same dosing schedule), if there is no evidence of disease progression as per irRC. A decision to resume treatment following the occurrence of a DLT is at the discretion of the Investigator. Following an AE meeting criteria for DLT, if a patient resumes study treatment, it should be at the next lower dose level. Dose reductions to doses below MCS110 0.3mg/kg / PDR001 100 mg Q3W are not permitted. If more than 2 consecutive doses have to be skipped due to study treatment-related toxicities, then the patient must be discontinued from the study unless the patient experiences clinical benefit in the opinion of the investigator. In this case, treatment can be continued at a dose agreed by Novartis and the investigator.
- For clinical management of suspected immune-related events, reference to consensus management guidelines is recommended such as those provided in the National Comprehensive Cancer Network (NCCN) Guidelines for the Management of Immunotherapy-Related Toxicities (available at : https://www.nccn.org/professionals/physician_gls/default.aspx#immunotherapy), the American Society for Clinical Oncology clinical practice guideline for Management of Immune-Related Adverse Events in Patients Treated With Immune Checkpoint Inhibitor Therapy (Brahmer 2018) or the European Society for Medical Oncology (ESMO) Clinical Practice Guidelines for Management of Toxicities from Immunotherapy (Haanen 2017). Note that in general, study treatment should be interrupted for grade 3 and 4 toxicities and for a subset of lower grade toxicities.

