Grade 2	Hold study treatment. Pulmonary and infection workup. Upon resolution to \leq Grade 1, may resume study treatment without dose modification
Grade 3 or 4	Discontinue study treatment.
Ocular (uveitis)	
Grade 1	Continue study treatment without dose modification. Ophthalmology consultation.
Grade 2	Hold study treatment. Urgent ophthalmology consultation. Upon resolution to \leq Grade 1 may consider resuming study treatment without dose reduction after discussion with the Novartis Medical Monitor and in consultation with ophthalmology

Toxicity	Dose Adjustment Rules*
Grade 3 or 4	Discontinue from treatment. Urgent ophthalmology consultation.
Periorbital edema	
Grade 2	Delay treatment until resolved to ≤ Grade 1. Decrease MCS110 1 dose level.
Grade 3-4	Discontinue from treatment.
Dermatology (rash)	
Grade 1	Continue study treatment without dose modification. Topical steroids, antihistamines, topical emollients
Grade 2	Consider holding study treatment. Topical or oral steroids, antihistamines. If study treatment is held and resolution to ≤ Grade 1, resume study treatment without dose modification.
Grade 3 or Grade 4	Hold study treatment. Manage per institutional practice. After resolution to ≤ Grade 1, consider resuming study treatment after discussion with the Novartis Medical Monitor.
Bullous dermatitis	Hold study treatment. Grade 1-2 bullous dermatitis: discussion with the Novartis Medical Monitor is required before considering resuming study treatment. Grade 3 bullous dermatitis: consider resuming therapy after expert consultation and documented discussion with the Novartis medical monitor. Grade 4 bullous dermatitis: discontinue study treatment.
Stevens-Johnson syndrome (SJS), or Lyell syndrome/toxic epidermal necrolysis (TEN)	Permanently discontinue study treatment.
Cardiovascular	
ECG QTc-Interval prolonged; hypertension	
Grade 3	Hold study treatment. Upon resolution to Grade ≤ 1 or baseline (hypertension, QTc) or < 30 msec difference from baseline (QTc) within ≤ 7 days, may resume study treatment without dose modification after discussion with the Novartis Medical Monitor. Baseline ECG refers to the ECG(s) collected at screening
Grade 4	Discontinue study treatment
Other cardiovascular disorders	
Grade 2 (except myocarditis)	Hold study treatment. Upon resolution to Grade ≤ 1 or baseline, may resume study treatment without dose modification after discussion with the Novartis Medical Monitor..

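### Section 6.3.1 allows dose modification in cycles 1–2 only after a DLT, but Table 6-4 requires an MCS110 decrease for Grade 2 periorbital edema, which is not a listed DLT

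*Protocol*

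**What the plan says.** The lead sentence of Protocol 6.3.1 lets doses be adjusted so that a patient can stay on treatment, "except during the first two cycles when dose modifications are only allowed if the patient experiences a DLT". It names neither study part.

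The first bullet of 6.3.1 then sends the reader to the table: "Dose modifications for toxicities related to the study medication are summarized in Table 6-4". Table 6-4 lists actions by event and grade, with no cycle limit and no requirement that the event be a DLT. For Grade 2 periorbital edema it requires a delay until recovery and then: "Decrease MCS110 1 dose level". The CK row ends with the same instruction after a Grade 3–4 elevation with abnormal cardiac markers, raised creatinine or symptoms. Other Grade 2 rows order a hold, for example pneumonitis: "Hold study treatment. Pulmonary and infection workup". The second bullet of 6.3.1 adds: "Note that in general, study treatment should be interrupted for grade 3 and 4 toxicities and for a subset of lower grade toxicities".

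Table 6-3 defines the DLTs. After the Grade 3 and 4 rules comes a short list under "The following Grade 2 AEs will be considered as DLTs", with three entries: bilirubin above 2 x ULN with Grade 2 or higher AST/ALT; pneumonitis lasting more than 7 days despite corticosteroids; and eye pain or reduced visual acuity that does not respond to topical therapy or needs systemic treatment. A discretionary clause follows: "Other clinically significant toxicities, including a single event or multiple occurrences of the same event may be considered as DLT's". One sentence of 6.2.4 limits DLTs to events "occurring in the first two cycles of treatment during the Phase Ib dose escalation part of the study".

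**The concern.** Read together, the lead sentence of 6.3.1 and the decrease rows of Table 6-4 give different answers for an early toxicity that is not a DLT. A site that lowers MCS110 in cycle 2 after Grade 2 periorbital edema follows the table and breaks the sentence. A site that keeps the dose does the reverse.

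Four analysis items depend on which rule was followed in Phase Ib:

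- **Dose in the BLRM.** Under SAP 2.5.2.1.1, a patient whose two doses in cycles 1–2 differ is counted at the lower one.
- **DDS membership.** A DLT-free patient needs two doses of MCS110 and PDR001 in the first two cycles (Protocol 10.1.4, SAP 2.2.3). A reduced dose is still a dose, but a skipped one can remove the patient.
- **Tolerability.** Interruptions and reductions are primary Phase Ib variables (Protocol 10.4.1).
- **Deviations.** The same reduction is compliance under one passage and a deviation under the other. All deviations are listed (SAP 2.3.1).

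**Working it through.** No figure of the plan is at issue, so the check sets the passages side by side.

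**1. Rows that change the dose level**

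- *Grade 2 periorbital edema.* Table 6-4 requires a decrease of one MCS110 level. It is not one of the three Grade 2 DLTs in Table 6-3, and the opening definition in 6.2.4 starts at Grade 3. A dose-level decrease is a dose modification on any reading, so the conflict in cycles 1–2 is direct.
- *CK elevation.* Table 6-3 has no CK exemption at Grade 4, so a Grade 4 elevation that meets the attribution conditions is a DLT and there is no conflict. At Grade 3, CK is exempt from DLT status when the investigator judges that there is no associated muscle damage. The Table 6-4 decrease can be triggered by raised creatinine or by symptoms alone. A Grade 3 case can therefore meet the decrease criteria without being a DLT, so the conflict is possible but depends on judgment.

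**2. Rows that mandate action at Grade 1–2**

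Rows that only ask the site to consider a hold, and the rows on stopping an infusion in progress, are left out. Fifteen rows remain:

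- 12 holds: diarrhea/colitis, AST/ALT, isolated bilirubin, pancreatitis, creatinine, other endocrine, pneumonitis, uveitis, bullous dermatitis, other cardiovascular, musculoskeletal, neurology
- 2 discontinuations: transaminitis with bilirubin above 1.5 x ULN, and myocarditis
- 1 delay with decrease: periorbital edema

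12 + 2 + 1 = 15. Three of these (transaminitis with bilirubin, pneumonitis, uveitis) overlap a listed Grade 2 DLT, and only under conditions. The other 15 − 3 = 12 do not.

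**3. Is a hold or a discontinuation a dose modification?**

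- *For:* the title of Table 6-4 and its column heading, Dose Adjustment Rules, cover every row. Section 6.3.1 describes the table's contents as dose modifications. The term is not defined.
- *Against:* nine of the 12 hold rows say to resume or continue without dose modification, and the uveitis row says without dose reduction (9 + 1 = 10 of 12). Section 6.3.1 has dose delay as a separate part of its title and itself directs interruption for some lower-grade events. Section 6.1.1 allows delays of up to 7 days for adverse events in any cycle. Section 7.1.3 lists an adverse event as a reason to discontinue. Section 8.1.1 records dose adjustment, interruption and discontinuation as separate actions.

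The weight is against, but the term stays open.

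**4. Phase II**

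The 6.3.1 restriction is not limited to a study part. By contrast, 6.4.1 confines its own cycle 1–2 rule on growth factors to dose escalation. In 6.2.4 one sentence limits DLTs to Phase Ib. The opening definition does not, and the heading of Table 6-3 also mentions cohort expansion. The scope is unclear.

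**5. Effect on the BLRM**

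Take a DLT-free patient assigned 5 mg/kg MCS110 with 300 mg PDR001 who has Grade 2 periorbital edema in cycle 1. One level down in Table 6-2 is 3 mg/kg with 300 mg. If the cycle 2 dose is reduced, the patient counts as DLT-free at 3/300; if not, at 5/300. The same event can thus inform different dose levels, depending on which passage the site followed.

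**6. Timing**

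The last patient was enrolled on 10-Jan-2019. Adding the 21-day screening window and 42 days for two cycles gives 63 days, or 14-Mar-2019 if dosing ran on schedule. On 08-Jul-2019, 179 days after that enrollment, 6 patients were still on treatment, all in Phase II.

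**The case against.** The strongest reply is that most of Table 6-4 does not conflict with 6.3.1. A reader might infer that the 15 rows all give sites opposite instructions, and that patients could be dosed through early immune toxicity. The documents do not support this. A hold followed by an unmodified dose is, in the table's own wording, not a dose modification, and the separate provisions on delay and discontinuation point the same way. The lead sentence concerns adjustments that let a patient continue, so it does not address discontinuation. Even the periorbital edema row requires a delay first; the conflict is over the dose at restart. This part of the objection stands, and it reduces the holds and discontinuations to a question of undefined terms.

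The discretionary DLT clause is also cited as a cure, since a site or the sponsor could declare the edema a DLT. That softens the conflict but does not remove it: the clause says such events may count, while the table row applies to every Grade 2 case. For CK the overlap between the decrease criteria and muscle damage is large, so that case is rightly called only possible.

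Finally, the analysis rules for unequal doses and for DDS membership are already stated. That is correct. They fix how an early reduction is handled once made, but not whether it should have been made.

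**Conclusion.** The contradiction is real but narrow. One row of Table 6-4 (Grade 2 periorbital edema) cannot be followed in cycles 1–2 together with the lead sentence of 6.3.1, and a second (Grade 3 CK) may conflict. For the 12 hold rows and 2 discontinuation rows the finding is ambiguity.

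Two further inferences should be resisted. One is that Phase II patients could never qualify for a modification in cycles 1–2: this relies on a single sentence of 6.2.4 and ignores the unrestricted opening definition and the heading of Table 6-3. The other is that all 60 + 81 = 141 treated patients were affected: that is everyone treated, whereas only those with such an event in the first 42 days met the conflict. The documents do not give that number. The periorbital edema reported from the earlier MCS110 studies in Protocol 1.2.2.2 was Grade 1.

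With enrollment closed and the early cycles over, the remaining effect is on deviation classification and the Phase Ib analysis, and little on patient care. The conclusion assumes that a dose-level decrease is a dose modification and that the edema was not separately declared a DLT. It takes no view on which clinical rule is right.

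**What to change.** In the protocol text or a clarification letter:

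- Reconcile the lead sentence of 6.3.1 with the dose-decrease rows of Table 6-4, and say which passage governs a non-DLT event in cycles 1–2.
- State whether the restriction covers dose-level changes only or also holds.
- State whether it applies in Phase II and, if so, how DLT is to be understood there.

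For patients already treated, record in the SAP or a note to file the interpretation used for early reductions and holds when classifying deviations, deciding DDS membership and assigning the BLRM dose. Listing any Phase Ib patient whose cycle 1–2 dose was reduced or skipped without a DLT would show whether the point affected the analysis.

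The cost is a few sentences of wording and one listing from dosing data already collected. Sample size and analysis methods are unchanged.

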- Consider early referral to specialists with expertise in the diagnosis and management of immune-related AEs to thoroughly investigate events of uncertain etiology.
- Events not included in the study protocol or the reference guidance documents should be managed per institutional preference.

- If one of the study drugs is discontinued the patient may continue with the remaining study drug, if the investigator considers it to be in the patient's best interest. The dose of the remaining study drug must be agreed by Novartis and the investigator.

Patients who discontinue the study treatment for a study related AE or a study-related abnormal laboratory value must be followed as described in [Section 6.3.2](#).

Table 6-4 Dose modification for drug related toxicities

Toxicity	Dose Adjustment Rules*
Hematology	
Neutropenia (ANC)	
Grade 3 or Grade 4.	Hold study treatment. Upon resolution to \leq Grade 2 or baseline within \leq 7 days, resume study treatment without dose modification, after discussion with the Novartis Medical Monitor
Febrile neutropenia	
Grade 3 or Grade 4	Hold study treatment. Upon resolution of fever and improvement of neutropenia to \leq Grade 2 or baseline, resume study treatment without dose modification, after discussion with the Novartis Medical Monitor.
Thrombocytopenia	
Grade 3	Hold study treatment. Upon resolution to \leq Grade 2 or baseline, resume study treatment without dose modification. For Grade 3 associated with major bleeding, discontinue study treatment.
Grade 4	Discontinue study treatment.
Anemia	
Grade 3 or Grade 4	Hold study treatment. Upon resolution to \leq Grade 2 or baseline within \leq 7 days, resume study treatment without dose modification.
Lymphopenia	
Any grade	Treatment-related lymphopenia does not require study treatment hold or discontinuation.
Gastrointestinal	
Diarrhea/colitis*	
Grade 1	May continue study treatment without dose modification. Manage per institutional standard guidelines which should include anti-diarrheal treatment, consideration of corticosteroid therapy, and hydration.
Grade 2	Hold study treatment. GI consultation. Upon resolution to \leq Grade 1 and tapering of steroid requirement to \leq 10 mg prednisone per day, resume study treatment without dose modification after discussion with the Novartis Medical Monitor.

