Grade 3	Hold study treatment. GI consultation. Upon resolution to \leq Grade 1 and tapering of steroid requirement to \leq 10 mg prednisone per day, consider resuming study treatment after discussion with the Novartis Medical Monitor.
Grade 4	Discontinue study treatment.

Toxicity	Dose Adjustment Rules*
Hepatic (AST and/or ALT elevation)	
Grade 2 AST and/or ALT	Hold study treatment. Manage per institutional practice. Upon resolution to \leq Grade 1 or baseline, consider resuming study treatment without dose modification.
Grade 2 transaminitis with bilirubin $>1.5 \times$ ULN (unless Gilbert's syndrome)	Discontinue study treatment.
Grade 3 AST and/or ALT	Hold study treatment. Manage per institutional practices. Upon resolution to \leq Grade 1 or baseline within 7 days, consider resuming study treatment without dose modification after discussion with the Novartis Medical Monitor. Otherwise, discontinue study treatment
Grade 4 AST and/or ALT	Discontinue study treatment.
Isolated total bilirubin elevation**	
Grade 2	Hold study treatment. Upon resolution to \leq Grade 1 or baseline, may continue study treatment without dose modification.
Grade 3	Hold study treatment. Upon resolution to \leq Grade 1 or baseline, may consider resuming study treatment after discussion with the Novartis Medical Monitor.
Grade 4	See footnote**. Otherwise, discontinue study treatment.
Asymptomatic amylase and/or lipase elevation***	
Grade 3 or Grade 4, not associated with symptoms or clinical manifestations of pancreatitis***	Continue study treatment. If levels do not resolve to \leq Grade 2 within \leq 14 days after the initial report, hold study treatment. Upon resolution to \leq Grade 2, may resume study treatment without dose modification, after discussion with the Novartis Medical Monitor.
Pancreatitis	
Grade 2 / radiologic evidence	Hold study treatment. Manage per institutional practice. Upon resolution to \leq Grade 1, may resume study treatment without dose modification, if no clinical evidence of pancreatitis and after discussion with the Novartis Medical Monitor.
Grade 3-4	Discontinue from treatment.
CK elevation	

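### For a dose-limiting toxicity that recovers within the 7-day delay limit, Protocol 6.3.1 and Table 6-4 give different resumption doses, and nothing says which governs

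*Protocol*

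**What the plan says.** - **Protocol 6.3.1, first bullet.** Treatment is withheld after an AE that meets the DLT criteria of 6.2.4. Whether to restart is left to the investigator, and recovery to Grade 1 or baseline is needed. On the dose: "Following an AE meeting criteria for DLT, if a patient resumes study treatment, it should be at the next lower dose level". The same bullet also sends the reader to the table: "Dose modifications for toxicities related to the study medication are summarized in Table 6-4".
- **Protocol 6.2.4 and Table 6-3.** The DLT window is the first two cycles of the Phase Ib part. "Any Grade 4 AEs will be considered DLTs with the exception of" is followed by two items: short neutropenia without fever or symptoms, and lymphopenia or leukopenia. "Any Grade 3 AEs will be considered DLTs with the exception of" is followed by a longer closed list.
- **Table 6-4, febrile neutropenia, Grade 3 or 4.** Once fever has resolved, the threshold and action are "Grade 2 or baseline, resume study treatment without dose modification, after discussion with the Novartis Medical Monitor".
- **Table 6-4, anemia, Grade 3 or 4.** Resume at the unchanged dose on recovery to Grade 2 or lower, or baseline, within 7 days.
- **Table 6-4, Grade 3 AST and/or ALT.** On recovery to Grade 1 or baseline within 7 days, "consider resuming study treatment without dose modification after discussion with the Novartis Medical Monitor". Otherwise treatment is discontinued.
- **Table 6-4 footnote and Protocol 6.1.1.** If a dose is delayed more than 7 days for an unresolved AE, it is skipped, and treatment restarts at a lower level if DLT criteria are met.
- **Protocol 10.4.1.** Dose interruptions, reductions and dose intensity are primary variables of Phase Ib.

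**The concern.** A DLT that has its own row in Table 6-4 falls under two instructions with different doses, and 6.3.1 refers to the table without ranking the two. A site can comply with one passage and depart from the other. The choice then shows up in the data as a dose reduction or none, and as a different dose intensity. These are the quantities by which Phase Ib tolerability is judged, so differences between dose levels or sites could partly reflect which passage was followed.

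**Working it through.** The documents give no figure on this point. The check sets the passages side by side and then illustrates the effect on the tolerability data.

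**Step 1. Which Table 6-4 events are DLTs?** The event must fall in the window and not be attributed to disease, intercurrent illness or concomitant medication.
- *Febrile neutropenia, Grade 3-4.* The Grade 3 fever exemption requires absence of neutropenia, and the Grade 4 neutropenia exemption requires absence of fever. Neither applies.
- *Anemia, Grade 3-4.* Named in neither list.
- *ALT, Grade 3.* Not named. The AST exemption covers only isolated AST elevation.
- A Grade 3 immune-related event that stays at Grade 3 for less than 7 days after corticosteroids is exempt. This can remove individual cases of any of the three, most plausibly ALT.

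**Step 2. What dose on resumption, for a DLT that is not exempt?**

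| Event | 6.3.1 | Table 6-4 row | Footnote and 6.1.1, delay of 7 days or less |
|---|---|---|---|
| Febrile neutropenia Gr 3-4 | next lower level, at Gr 1 or baseline | unchanged dose, at Gr 2 or lower or baseline | silent |
| Anemia Gr 3-4 | same | unchanged dose, at Gr 2 or lower or baseline, within 7 days | silent |
| ALT Gr 3 | same | unchanged dose may be considered, at Gr 1 or baseline, within 7 days | silent |

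For a delay over 7 days, the footnote and 6.3.1 both lead to a lower level. For a shorter delay, 6.3.1 and the row disagree on dose in all three lines. In the first two they also disagree on the recovery threshold.

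**Step 3. Effect on the recorded data.** SAP 2.4.1 defines RDI as DI/PDI, each divided by the same number of scheduled doses. RDI is therefore cumulative dose over cumulative planned dose. Assume the DLT follows dose 1, all doses are given on schedule, and the dose drops one step from dose 2 onward. For n doses:

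RDI = [full + (n − 1) × reduced] / (n × full)

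- No change of dose: RDI = 1.00 (category 0.9 to <1.1), no reduction counted.
- MCS110 10 to 5 mg/kg: n = 2, 15/20 = 0.75; n = 6, 35/60 = 0.58; n = 12, 65/120 = 0.54.
- MCS110 5 to 3 mg/kg: n = 2, 8/10 = 0.80; n = 6, 20/30 = 0.67; n = 12, 38/60 = 0.63.
- PDR001 300 to 100 mg: n = 2, 400/600 = 0.67; n = 6, 800/1800 = 0.44; n = 12, 1400/3600 = 0.39.

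These steps are those of Table 6-2. A 7.5 mg/kg level was also used in the study. If that is the next level below 10 mg/kg, six doses give (10 + 5 × 7.5)/60 = 47.5/60 = 0.79. In every case the patient leaves the 0.9 to <1.1 category, and one dose reduction is added under the SAP definition.

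**The case against.** **Scope of the DLT rule.** Section 6.3.1 is triggered by criteria in 6.2.4, which are confined to the first two cycles of Phase Ib. One can read 6.3.1 as governing that window and Table 6-4 as governing everything else. This stands as a limit on scope. It does not settle the matter inside the window, because the DLT bullet itself points to Table 6-4 and the table's footnote uses DLT criteria.

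**Timing.** The Amendment 04 status lists 6 + 12 + 12 + 13 + 6 + 11 = 60 patients by 10 April 2018, which is the whole escalation part. A 42-day window from that date ends about 22 May 2018, barring delays. Section 6.3.1 and Table 6-4 were updated in Amendment 04, dated 20 July 2018. No Phase Ib DLT window therefore appears to have been open under the current table, and its earlier rows cannot be seen here. By 08-Jul-2019 only 6 patients, all in Phase II, were on treatment. This stands: an edit now cannot alter Phase Ib dosing.

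**Safeguards.** The febrile neutropenia and ALT rows require discussion with the sponsor's medical monitor, and 6.2.3.1 has every DLT agreed at the dose-decision teleconference. This reduces site-to-site variation. It does not say which dose applies, and the anemia row has no such step.

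**The ALT row.** It only permits the unchanged dose, and it overlaps the Table 6-3 exemptions for isolated AST and short steroid-treated immune-related events. This stands, so only the remaining Grade 3 ALT cases are counted.

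**The footnote.** It hangs on the column heading and so qualifies every row, but only for delays over 7 days.

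**Conclusion.** The contradiction is real and narrow. It concerns a DLT in the first two cycles of Phase Ib that recovers within the 7-day delay limit. It is clear for Grade 3-4 febrile neutropenia and anemia, and conditional for Grade 3 ALT elevation outside the Table 6-3 exemptions. In those cases one event can be recorded with or without a reduction. The illustrated RDI over 2 to 12 doses is 0.75 to 0.54 for MCS110 10 to 5 mg/kg, against 1.00 if unmodified. The number of patients affected is unknown.

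A reader might infer more than the documents support:
- *That Phase II summaries are affected.* Whether meeting DLT criteria counts in later cycles or in Phase II is not stated.
- *That patient safety was directly affected.* No affected patient is shown, and Phase Ib dosing appears to predate the current table.
- *That every row allowing the unchanged dose conflicts.* Several match Table 6-3 exemptions, such as Grade 3 thrombocytopenia without significant bleeding.

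Two further rows deserve the same check but are not counted here: asymptomatic Grade 3-4 amylase or lipase elevation, where treatment continues at first, and Grade 2 pneumonitis, which Table 6-3 makes a DLT under the condition "Pneumonitis persisting > 7 days despite treatment with corticosteroids".

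**What to change.** Reconcile Protocol 6.1.1 and 6.3.1 with Table 6-4 and its footnote, for both the resumption dose and the recovery threshold. State which passage governs when an event meets DLT criteria and also has its own row. State whether the rule applies after the first two cycles and in Phase II. The choice of rule is a clinical one for the sponsor and investigators.

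The cost is a sentence or two and edits to a few table rows. Because Phase Ib dosing is complete, the study report could also say which rule was applied to each DLT after which treatment was resumed, so that reductions and dose intensity can be read correctly.
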